Enrollment/ Randomization assignment to H42-HV or mHIP-HV	
 • Once the participant has completed the baseline survey and has registered one weight on the home study scale, research staff will schedule a mutually convenient time for the randomization visit. The randomization procedure will follow similar procedures to those established for our ongoing pragmatic trial (IRB00307430). • Randomization must be complete by 34-weeks gestation.

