9. DATA COLLECTION AND MEASUREMENTS

9.1. Overview of measures, instrument and data sources

Table 3 summarizes the measures (with references to the standard instruments) we will use and the timing of data collection aimed at minimizing participant burden. Data will be collected using 4 methods: online surveys, home scale, medical record review, and Medicaid claims data.

Measures and Instruments	Data source(s)	Timing				
		BL	36-38wk	2 mo	4 mo	6 mo
Demographics, preferred language, acculturation, & medical history ^{58,59}	Online (+ phone assisted) surveys	x				
Discrimination experiences ⁶⁰	Online (+ phone assisted) surveys	x				
Postpartum weight retention (PPWR)	Pre-pregnancy height & weight (prior to 15 wks) from medical records	x				
Gestational weight gain (GWG)	37-weeks & postpartum weights from home scale		x	x	x	x
Safety net services & home visiting care utilization and experiences	Online (+ phone assisted) surveys	x	x	x	x	x
Maternal health care utilization	Claims + Online (+ phone assisted) surveys		x	x	x	x
Health behaviors (diet ^{61,62} ; physical activity ⁶³ ; alcohol, marijuana, tobacco use ⁵⁸ ; breastfeeding ⁶⁴)	Online (+ phone assisted) surveys	x	x	x	x	x
Maternal wellness (depression ⁶⁵ , stress ⁶⁶ , sleep ⁶⁷ , social supports ⁶⁸)	Online (+ phone assisted) surveys	x	x	x	x	x
Infant weight and length (birth weight and 2, 4, and 6 months weights)	Online (+ phone assisted) surveys & medical records			x	x	x
Infant health care utilization	Claims + Online (+ phone assisted) surveys			x	x	x

Abbreviations: BL=baseline; mo=months postpartum; wk=weeks gestation.

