We will carry out the main analysis to assess the between group difference using a mixed effects model characterized by a mean model relating the outcome to the predictors and a variance-covariance model addressing variance of all available longitudinal weight outcomes and correlation between outcomes measured overtime within individual. The predictors in the mean model will include a group indicator (0 for Group B and 1 for Group A), 3 visit indicators for 2, 4, and 6 months respectively, with 0 for baseline and 1 for the specific month postpartum the visit indicator corresponding to, and the group by visit interaction terms, adjusting for study sites, BMI category, and gestation at the time of enrollment used for randomization stratification, all as fixed effects. The regression coefficient of the group by 6-months postpartum weight interaction term will estimate the primary outcome, i.e., mean difference in PPWR at 6-months between intervention and control groups. We will use an unstructured variance-covariance model to allow full flexibility on outcome variances and correlations. Data from all participants randomized will be used in this analysis, including missing data which will be included using a software specified missing indicator.

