16.0. Sample Size and Power Estimates informing Primary Aim

We request approval for enrollment up to 400 participants with the goal of N=360 for power calculations.

Table 6. MDD for PPWR for sample of 360 with 90% power, after 30% random attrition

Power	SD of PPWR (Kg)	Minimum Detectable Difference (MDD) (Kg)
90%	5.5	2.26
90%	7.0	2.87
90%	8.0	3.28
90%	8.8	3.61

With this sample size, our objective is to determine the minimum detectable difference (MDD) for the primary outcome of PPWR between the 2 study groups. Our assumptions are as follows: Two-sided type I α error=0.05; type II β error=0.10; and 70% or greater follow-up for the main outcome of PPWR at 6-months. Based on our past experience and review of the literature, we anticipate <30% loss to follow-up for 6-month weights, consequential to drop-out of various kinds (e.g., lost to follow-up, censored due to new pregnancy). With this dropout rate and the assumption that the dropout is consistent with missing at random,

we expect to retain an effective sample size of 252 participants for our primary outcome, by randomizing N=360 participants, with 126 participants in each arm. Standard deviations for the MDD evaluation were informed by previous studies of similar combined diet-physical activity behavioral interventions to limit weight gain in pregnancy and promote postpartum weight loss^{88,89,90,91}. The MDDs range from 2.3- 3.6 kg with the assumption of 30% random attrition of the proposed sample size of 360. Based on these prior studies effect sizes we believe our sample size calculation in **Table 6** is conservative.

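### The primary model omits the 37-week weight and no analysis examines departures from missing at random, so the PPWR difference is open to a modest bias, in either direction, if gain-related loss differs by arm

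*Combined protocol and SAP*

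**What the plan says.** Table 3 (Section 9.1) lists "37-weeks & postpartum weights from home scale", and the home-scale section (the second one numbered 9.2) schedules maternal weights at 37 weeks and at 2, 4 and 6 months postpartum.

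The primary mean model in Section 15.2 takes baseline as the reference level and has "3 visit indicators for 2, 4, and 6 months respectively", each interacting with group. The group-by-6-month term is the primary estimate, and the covariance is unstructured. Section 15.3 sends gestational weight gain to a separate model. Section 15.2 also says that the covariance model covers all the longitudinal weights available. That does not bring the 37-week weight in: without an indicator of its own, it would be coded as a baseline value.

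On missing data, Section 15.2 keeps all randomised women in the likelihood model, with a software code for missing values. Section 16.0 plans for "70% or greater follow-up for the main outcome of PPWR at 6-months" and rests on "the assumption that the dropout is consistent with missing at random". Section 17 has the only sensitivity analysis, which concerns outliers; outliers that are removed become missing values as well. The plan names no delta-adjusted, tipping-point, pattern-mixture or imputation analysis.

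**The concern.** A woman lost before her 2-month weight gives the primary model only her early-pregnancy weight, even where the trial holds her 37-week weight. Gestational gain should predict retention, and Table 4 makes it a target of the intervention. If gain also predicts loss, leaving it out makes missing at random harder to defend than it need be.

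What matters for the arm comparison is whether the link between gain and loss differs between arms. The protocol makes that plausible. Participants are unblinded (Section 11). Only H42-HV has coaching calls, and coaches contact home visitors when calls are missed (Section 12.1.e). Non-compliance with the study intervention is a ground for discontinuation (Section 14.1), which bears mainly on H42-HV. At stake is a distortion of the primary estimate that collected data could partly remove, and a result whose dependence on the missing-data assumption the reader cannot judge.

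**Working it through.** **1. The plan's own figure.** Inputs from Section 16.0: "Two-sided type I α error=0.05; type II β error=0.10"; 360 × 0.70 = 252 retained, 126 per arm; SD 5.5, 7.0, 8.0 and 8.8 kg. The standard error of the difference is SD × √(2/126), which is 0.88 kg at SD 7.0. The normal formula gives (1.960 + 1.282) × 0.882 = 2.86 kg. The noncentral t with 250 df gives 2.255, 2.870, 3.280 and 3.608 kg, against the stated 2.26, 2.87, 3.28 and 3.61. Table 6 reproduces. It allows for the precision lost through attrition, not for bias.

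**2. Assumed inputs, not in the documents.** SD 7 kg for gain (for PPWR it is one of the Table 6 values); correlation r of gain with 6-month PPWR 0.4 to 0.6; loss p = 0.30 in each arm; odds ratio (OR) of loss 1.5 to 2 per SD of gain in one arm and 1 in the other; the share of losses before the 2-month weight.

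**3. Hand check.** To first order, with all loss before 2 months, mean PPWR in the affected arm shifts by ln(OR) × p × r × SD.

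- OR 2: 0.693 × 0.30 × 7 = 1.46; times r = 0.58 to 0.87 kg.
- OR 1.5: 0.405 × 0.30 × 7 = 0.85; times r = 0.34 to 0.51 kg.
- Scaled by an early share of 50 to 80%: 0.5 × 0.34 = 0.17 kg up to 0.8 × 0.87 = 0.70 kg.

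This overshoots somewhat at the upper end, so the simulated values below are the ones to use.

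**4. Simulation.** Maximum-likelihood fit of the unstructured model, 200,000 women per scenario, Monte Carlo error about 0.03 to 0.04 kg. Entries are absolute bias in the arm difference (kg).

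| Link of gain with loss | Share lost before 2 months | Planned, r 0.4 | Planned, r 0.6 | With 37-week weight |
|---|---|---|---|---|
| OR about 2, one arm | one third | 0.05 | 0.18 | 0.02 |
| OR about 2, one arm | two thirds | 0.30–0.34 | 0.41–0.54 | at most 0.07 |
| OR about 1.5, one arm | two thirds | 0.10 | 0.32 | at most 0.07 |
| OR about 2, both arms | two thirds | 0.03 | at most 0.08 | at most 0.06 |

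The 0.10 entry is partly noise: the same run with the 37-week weight gave −0.07, so the two fits differ by 0.10 + 0.07 = 0.17 kg. A second simulation (n = 360, 1,500 replicates, no true effect, 50 to 80% early loss, OR 1.5 to 2 in one arm) gave 0.16 to 0.61 kg. Adding the 37-week weight cut this to 0.04 kg or less and lowered the standard error by 0.5 to 4.5%.

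The sign depends on the arm. Loss of high gainers in H42-HV only favours H42-HV (−0.32 kg at r 0.4, two thirds early); the same loss in the comparison arm works against it (+0.30 kg).

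**5. Limit of the remedy.** If half of the early losses also precede the 37-week weight (OR 2, 65% of losses early), 0.13 to 0.20 kg of 0.28 to 0.45 kg remains, about half.

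**6. What the bias does (SD 7, standard error 0.88 kg).** At 0.18 kg, two-sided type I error is 0.055, and power at 2.87 kg is 0.86 if the bias is toward the null. At 0.30 kg they are 0.063 and 0.83; at 0.45 kg, 0.080 and 0.78. At 0.6 kg, 0.6/0.882 = 0.68, so type I error is Φ(−1.28) + Φ(−2.64) = 0.10.

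**7. Departures from missing at random.** With 30% lost, a shift of d kg among the missing women of one arm moves the difference by 0.30 × d. An observed difference of 2.87 kg loses significance at d = (2.87 − 1.96 × 0.882)/0.30 = 3.8 kg, with the standard error held fixed. For SD 5.5, 8.0 and 8.8, with differences equal to the stated detectable ones, d is about 3.0, 4.4 and 4.8 kg.

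**The case against.** A likelihood model on baseline and postpartum visits is a standard choice, and an auxiliary visit is a refinement of it. The 30% is a ceiling ("we anticipate <30% loss to follow-up for 6-month weights"), scales transmit automatically, and Section 14.0 asks women who discontinue for their remaining assessments. The documents do not give the timing of losses, and one cause of loss named in Section 16.0, a new pregnancy, can hardly precede the 2-month weight. All of this stands. It is why the one-third-early range belongs beside the larger one, and why these figures are a range and not a prediction.

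Three stronger readings are tempting, and the documents support none of them.

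- That gain-related loss by itself biases the comparison, or favours H42-HV. It must differ by arm, and nothing says in which arm it would be stronger.
- That the collected weights would fully correct the problem. Every randomised woman "has registered one weight on the home study scale", so capture at 37 weeks is feasible. But no completion rate is given, and women lost or delivered before that weight will not have it.
- That the plan should test missing at random. Observed data cannot do so; what is absent is an analysis of departures from it.

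What the objection does not answer is that an outcome-related weight is collected and left out, and that the missing-data assumption is not varied at all.

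**Conclusion.** The point holds in a conditional form and should be addressed. The omission of the 37-week weight and the absence of a missing-data sensitivity analysis are plain in the text. A bias in the PPWR difference follows only if the link between gain and loss differs by arm.

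Under the assumptions in step 2, it is roughly 0.05 to 0.2 kg with one third of losses before 2 months and 0.16 to 0.6 kg with 50 to 80%. That is up to about 0.6/2.87 = 21% of the detectable difference at SD 7. With the same link in both arms it is about zero. The sample size in Section 16.0 is not in question.

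**What to change.** Amend Section 15.2 to add the 37-week weight as a further response visit in the same unstructured model, with its own visit indicator and group-by-visit term, and keep the group-by-6-month term as the primary estimate. It should enter as a response and not as a covariate: gain is measured after randomisation and is targeted by the intervention, so adjusting for it would remove part of the effect.

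As a supplement, prespecify an analysis that shifts missing 6-month weights by arm-specific amounts, for example 0 to 4 kg, and reports the shift at which the conclusion changes. Tabulating losses by arm, and by whether they precede the 37-week or the 2-month weight, would show how far the first change can help.

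The cost is SAP wording, one more row in the covariance matrix and a little extra analysis. No new data or change in sample size is needed. The wording should be settled before anyone sees outcomes by arm.

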15.3. Secondary outcomes and additional analyses

Analyses for between group differences in GWG and infant weights will be assessed using the same mixed-effects modeling approach with separate models similar to the main model described above. Between group differences in binary outcomes of diet, physical activity, breastfeeding and women's wellness outcomes (depression, sleep, stress, social support) will be described between H42-HV intervention and Control arms using standard cut points for the

scales and modeled using logistic regression model based longitudinal models implemented through generalized estimation equations (GEE) approach employing group indicator, visit indicators, group by visit interaction terms and adjusting for the variable used to stratified the randomization. Robust variance estimate will be used for statistical inferences to derive 95% confidence intervals for the population-average based estimates and corresponding p-values. Conforming to recommended maternal postpartum care utilization and well-baby care utilization over time will separately be modelled using similar GEE approach as described above for the longitudinal binary outcomes.

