15.4. Exploratory analyses for heterogeneity of intervention effect

Importantly, we will explore for potential modifiers of intervention effects by conducting subgroup analyses by race/ethnicity, HV program characteristics, baseline BMI category (overweight/obese), language spoken at home, low English proficiency, education level and exploring for effect modification by adding appropriate interaction terms to the primary mixed-effects model. Although we do not expect the main effects to differ, we will explore for the potential of such heterogeneity of intervention effect.

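### As listed, the primary model does not cross the randomisation strata with visit, so its strata adjustment has almost no effect on the 6-month weight change

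*Combined protocol and SAP*

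**What the plan says.** Section 15.2 treats baseline weight as one of the responses. The visit coding is "3 visit indicators for 2, 4, and 6 months respectively, with 0 for baseline and 1 for the specific month postpartum", with an unstructured covariance across the four weights. The mean model contains group, visit and group-by-visit, "adjusting for study sites, BMI category, and gestation at the time of enrollment used for randomization stratification, all as fixed effects". The primary result is a single coefficient: "The regression coefficient of the group by 6-months postpartum weight interaction term will estimate the primary outcome". On the analysis set, "Data from all participants randomized will be used in this analysis".

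No section names a stratum-by-visit term. Section 15.4 speaks of "adding appropriate interaction terms to the primary mixed-effects model", but only to explore effect modification. Section 11 confirms that site, BMI category and gestational age at enrolment are the randomisation strata. Section 16.0 rests on "the assumption that the dropout is consistent with missing at random" and says "we expect to retain an effective sample size of 252 participants for our primary outcome". Section 15.3 extends the method to secondary outcomes: "differences in GWG and infant weights will be assessed using the same mixed-effects modeling approach".

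**The concern.** The primary coefficient is a between-arm difference in change from baseline. A covariate that enters as a constant over visits describes the level of weight, not its change. Listing the strata in that form therefore looks like an adjustment but does not adjust the quantity being tested.

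Three things are at stake. First, readers will take the primary result as adjusted for the stratification factors when it is nearly the raw difference in change. Second, stratified randomisation balances these factors between arms. If they predict weight change and the model for change omits them, the model SE is too wide and the test is conservative. Third, up to 30% of 6-month weights may be missing and participants know their arm (Section 11). If dropout differs by arm and stratum together, the listed terms do not give the protection that the missing-at-random assumption relies on.

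**Working it through.** **Inputs from the documents.** N = 360 for power, 30% loss, 126 per arm analysed, two-sided alpha 0.05, power 90%, SD 7.0 kg with a minimum detectable difference of 2.87 kg (Section 16.0, Table 6). Allocation is 1:1 in blocks of 2, 4 and 6 within strata (Section 11).

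**Assumed, because the documents do not give them.** Share R² of the variance of 6-month change explained by the strata: 0, 5, 10, 20%, split BMI 1/2, site 1/4, gestation 1/4. Nine unequal sites (Section 7 names nine programs as examples) and two gestation categories. SD of change 5.5, 6.3 and 7.0 kg at 2, 4 and 6 months, residual correlations 0.75–0.85. BMI categories 20 kg apart at baseline.

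**1. The plan's own figure.** (1.96 + 1.2816) × 7.0 × √(2/126) = 2.86 kg by the normal approximation; the noncentral t gives 2.870 kg. Table 6 reproduces. It uses the raw SD and takes no credit for adjustment.

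**2. Algebra.** Write the listed model for woman i at visit t as

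Y_it = μ + γg_i + τ_t + δ_t g_i + s_i′β + e_it, with τ_0 = δ_0 = 0.

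Then Y_i6 − Y_i0 = τ_6 + δ_6 g_i + (e_i6 − e_i0). The stratum term s_i′β has gone. Replacing the four weights by baseline and three changes is one-to-one and keeps the covariance unstructured. The change equations contain group only; the baseline equation contains group and strata. With complete data, generalised least squares for the change equations is then ordinary least squares on group, and the estimate of δ_6 is the raw difference in mean change, with or without the strata.

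**3. Complete data, simulated** (REML, 20 datasets, R² 10%). The largest difference between no strata and listed strata was 1e-12 kg. Mean SE: 0.744 (none), 0.744 (listed), 0.703 (strata-by-visit).

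**4. 30% random dropout** (15, 22.5 and 30% missing by 2, 4 and 6 months; true difference 2.87 kg; 6,000 trials per R²; Monte Carlo error about 0.3 points per rate).

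| R² | Mean shift from adding listed strata (kg) | SE none / listed / by-visit | Type I error, listed | Power, listed | Power, by-visit |
|---|---|---|---|---|---|
| 0 | 0.02 | 0.830 / 0.830 / 0.834 | 5.4% | 92.6% | 92.3% |
| 5% | 0.03 | 0.828 / 0.828 / 0.813 | 4.75% | 93.0% | 93.6% |
| 10% | 0.04 | 0.826 / 0.827 / 0.791 | 4.4% | 93.5% | 94.6% |
| 20% | 0.05 | 0.822 / 0.824 / 0.746 | 3.7% | 94.6% | 96.7% |

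The largest single shift was 0.25 kg. By-visit type I error was 5.25% at every R², because the same seeds were used and that model is unaffected by additive stratum effects. Power exceeds 90% because the mixed model uses the earlier weights of women who drop out. With 10% of baseline weights also missing at random (R² 10%, 2,000 trials), the listed terms moved the estimate by 0.06 kg on average (largest 0.28 kg) and the SE by 0.2%.

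**5. Formula check** (complete balance, no use of intermediate weights). Type I error = 2[1 − Φ(1.96/√(1−R²))]; listed power = Φ(1.2816/√(1−R²)); by-visit power = Φ(3.2415/√(1−R²) − 1.96).

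- R² 5%: 4.4%; 90.6% v 91.4%, so 0.8 points unused.
- R² 10%: 3.9%; 91.2% v 92.7%, so 1.6 points unused (before rounding).

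**6. Dropout depending on arm and stratum** (by BMI category, reversed between arms; truth −2.87 kg; 2,000 trials each; Monte Carlo error 0.02 kg).

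| Dropout | R² | None | Listed | By-visit | Bias, listed |
|---|---|---|---|---|---|
| 45% v 15% | 10% | −2.68 | −2.54 | −2.88 | 0.33 |
| 45% v 15% | 5% | −2.74 | −2.64 | −2.88 | 0.23 |
| 37.5% v 22.5% | 10% | −2.79 | −2.72 | −2.89 | 0.15 |
| 37.5% v 22.5% | 5% | −2.82 | −2.77 | −2.89 | 0.10 |

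In all four cases the listed terms did worse than no strata terms. A likely reason is that, without strata, baseline weight itself carries some information on BMI category into the prediction of missing changes; the listed terms remove that information from baseline and put nothing into the change equations. The sign is not fixed: another 45% v 15% simulation (R² 10%, 300 trials, Monte Carlo error 0.04 kg) gave −3.00 (none), −3.17 (listed) and −2.81 (by-visit).

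**The case against.** The strongest reply is that little is lost. With complete data or random dropout the estimate is unbiased, the error is on the conservative side, and the listed model has at least 92.6% power in these simulations. At R² 5% the simulated type I error of 4.75% cannot be told apart from 5%, and the formula in step 5 overstates the conservatism under the planned dropout. If the strata predict nothing, the remedy costs a little power. All of this stands, and so does the point that R², the correlations and the gap between BMI categories are assumptions.

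The bias cases are also constructed. Nothing in the plan predicts dropout that reverses by BMI category between arms, and Section 16.0 also calls attrition random. The worst bias, 0.33 kg, is about 0.4 of an SE of 0.83 kg. That limits how much weight these cases can carry, but missing at random does allow such patterns.

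Finally, the wording in Section 15.2 could be meant to include strata-by-visit terms, since no full formula is given, and Section 15.4 is weak evidence either way because it concerns effect modifiers. But Section 15.2 spells out group-by-visit and no stratum interaction. A programmer following it would fit strata as main effects. If more was intended, the text needs to say so.

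**Conclusion.** The point holds. Read as listed, the strata adjustment drops out of the primary contrast exactly with complete data and almost entirely under random dropout. That part is algebra and does not depend on the assumed inputs.

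The practical cost under random dropout is small: no bias, a mildly conservative test if the strata predict change, and 0.6 to 1.1 points of unused power at an assumed R² of 5–10% (2.1 points at 20%; a loss of about 0.35 points from the fix at 0%). Under dropout that depends on arm and stratum, near-equality with the unadjusted result no longer holds, and the listed model can be biased by a few tenths of a kilogram; size and sign depend on the pattern assumed. Table 6 is not affected. The plan should be corrected, mainly so that the reported adjustment is real, but the trial's power does not hang on it.

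**What to change.** Keep baseline weight as a response, so that every randomised woman stays in the model, and add site-by-visit, BMI-category-by-visit and gestation-by-visit terms to the fixed effects in Section 15.2. State the gestation categories used and a rule, fixed before unblinding, for pooling small sites. Do the same for gestational weight gain if it is modelled as a change from a baseline response row; Section 15.3 does not settle that.

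This is a wording change with no new data. With nine sites and two gestation categories it adds 8 × 3 + 1 × 3 + 1 × 3 = 30 parameters, of which 8 + 1 + 1 = 10 bear on the 6-month contrast. If the strata predict nothing, the mean SE rises from 0.830 to 0.834 kg, about half a percent. The programs in Section 7 are only examples, so more or smaller sites would raise this cost; hence the pooling rule.
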